In this study, we will administer Fluzone® High-Dose vaccine with a planned booster to patients with monoclonal gammopathies irrespective of age versus a standard of care control group. Primary endpoint is composite of documented influenza infection rate and disease progression (as defined by International Myeloma Working Group criteria) at the end of the flu season. Based on the background data, we expect a higher rate of success in the experimental arm. As such, we power for success rates of 90% and 70% in the experimental and control arms, respectively. We will also analyze several secondary endpoints including rates of influenza related morbidity, the analysis of humoral and cellular immune response to these vaccines and the rate of disease control (defined as lack of disease progression by standard international myeloma working group criteria).

By comparing this experimental approach directly to standard of care, data from estimates of effectiveness will inform the design of larger future controlled studies. As such, the data from this study can lead to practice-changing results. The data on immune correlates will also yield important information about *in vivo* "immune-competence" of these individuals, which in turn is important to design trials with emerging immune therapies.

STUDY Endpoints:

Primary:

- 1) The primary clinical endpoint of this study is: to measure a composite of documented influenza infection rate and disease progression (as defined by International Myeloma Working Group criteria) at the end of the flu season following a high dose influenza vaccine booster strategy versus standard of care.

A Comprehensive Cancer Center Designated
by the National Cancer Institute

Phase: II

YCC Version 4.0 Date: 31-May-2017

pg. 8

Secondary:

1. evaluate rates of serologic protection (defined as HAI titer >40) following Fluzone® High-Dose influenza vaccine with booster dosing versus standard of care.
2. measure T cell subsets and flu-specific T cell responses following high dose influenza vaccine booster dosing strategy versus standard of care.

STUDY DESIGN:

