Although routinely used in adults 65 and older, no one had studied high dose flu vaccine specifically in patients with monoclonal gammopathies. Fluzone® High-Dose has been widely used since 2009 and demonstrated to be safe. Knowing that high dose influenza vaccine increases serologic protection in adults over 65, our study population may benefit as well, given the similar but more significantly depressed cellular immunity in patients with monoclonal gammopathies. With this in mind, we have already designed the recent SHIVERING Pilot study at Yale New Haven Hospital over the 2014-2015 flu season. In this pilot study, all patients received Fluzone® High-Dose with a second booster dose after 30 days. Enrollment has closed and data analysis is ongoing. However, preliminary data revealed that all 51 patients enrolled tolerated the two vaccine doses well and no grade 2 or above adverse events related to vaccine were reported. In addition, with very close follow-up 2/51 patients (4%) patients developed documented flu infections despite an expected rate of 20% in this population (manuscript in preparation).

Rationale for Treatment in this Setting

Sensing of pathogens by the immune system is mediated by family of distinct pattern recognition receptors (such as toll like receptors, TLRs) that then activate immune response. In the setting of tumors involving the immune cells themselves, such as multiple myeloma, tumor cells commonly express TLRs and signaling via TLRs has been shown to regulate the growth and survival of tumor cells. For example, infectious particles can activate TLRs and cause proliferation of myeloma cell lines and secretion of IL-6 (a potent myeloma growth cytokine)¹⁶. This has led to the hypothesis that exposure to common pathogens may itself contribute to promoting the growth of tumor cells. Unfortunately, these patients also have immune paresis and are at increased risk for infections. Prevention of major seasonal infections may therefore have major impact not only on infection-related morbidity, but also tumor growth. In addition to potentially direct effect on tumor cells, pathogen-related morbidity also leads to interruption of therapy, which may further compromise disease control.

A Comprehensive Cancer Center Designated
by the National Cancer Institute

Phase: II

YCC Version 4.0 Date: 31-May-2017

pg. 13

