Ultimately if this novel vaccine strategy proves to be more effective, an important question will be if mortality will also be improved. As discussed above influenza infections are associated both with their own morbidity and mortality, and may have a negative impact on disease control, thereby indirectly increasing mortality. All-cause mortality as a clinical endpoint will take into account all possible relation of influenza infections to mortality. One year estimates are known for patients with plasma cell disorders. The most recent SEER data of one year survival for newly diagnosed myeloma, based on patients diagnosed in 2009 is 79.2%.¹⁷ Relapsed refractory patients have lower survival depending on many risk factors and is estimated as low as 60-66%.^{18,19} MGUS patients are not believed to have much of a decrease in survival compared to age-matched controls and one-year survival is estimated to be 98%.²⁰ Most of the patients seen at Smilow cancer Hospital are relapsed/refractory multiple myeloma patients. We anticipated that more than 2/3 of patients enrolled will be relapsed / refractory and less than 1/3 will be MGUS or newly diagnosed plasma cell disorder patients. As would be expected, relapsed patients have reduced time to progression with each successive line of therapy. Kumar, et al²¹ followed 355 myeloma patients who have had at least two lines of therapy and showed that time to progression shortened with each line of therapy from 9.9 months after first therapy to 7.3 months after second therapy to less than 4 months after sixth line of therapy (see Figure 1 below). In our population of patients of relapsed patients mixed with newly diagnosed and early disease patients a conservative estimate of the proportion who would relapse from the time of initial vaccine to the end of the influenza season (which may range from roughly 4-8 months depending on when the patient receives their initial vaccine) is 10%. Considered together with an expected influenza infection rate of 20%, we would expect our control arm to have a combined disease progression and influenza infection rate of 30% (10%+20%).

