The principal investigator is responsible for monitoring the data, assuring protocol compliance, and conducting the safety reviews at the specified frequency [monthly]. During the review process the principal investigator will evaluate whether the study should continue unchanged, require modification/amendment, or close to enrollment.

The principal investigator, the Institutional Review Board (IRB), Yale Cancer Center Data and Safety Monitoring Committee (DSMC) have the authority to stop or suspend the study or require modifications.

This protocol presents minimal risks to the subjects and adverse events or other problems are not anticipated. In the unlikely event that such events occur, Reportable Adverse Events (which are events that are serious or life-threatening and unanticipated (or anticipated but occurring with a greater frequency than expected) and possibly, probably, or definitely related) or unanticipated problems involving risks to subjects or others will be reported in writing to the IRB (using the appropriate forms from the website) and any appropriate funding and regulatory agencies per IRB policy 710. The investigator will apprise fellow investigators and study personnel of all adverse events that occur during the conduct of this research project [via email as they are reviewed by the principal investigator.]

Biostatistical Considerations

The primary endpoint of this randomized Phase II study is a composite measure of two clinical endpoints. A patient is considered a treatment failure if either of the following events occur during the 2015-6 flu season:

- Progression of the underlying plasma cell disorder
- Any documented flu infection

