We plan to enroll 50 patients in the standard care group and 100 in the vaccine group for a total of 150. Patients will be separately allocated in this 1:2 ratio based on their disease type of early disease versus active disease in order to maintain balanced stratification between the groups. For each disease type, this 1:2 ratio will be performed in blocks of three in order to maintain balance in the study at all times. A randomization schedule will be prepared by the study biostatistician, [name], in advance of the trial beginning. If the standard care group has 0.70 probability of success (defined above) and the vaccinated group has probability of success equal to 0.90 then the power of this design is 0.93. As another example, if the standard care group has 0.75 probability of success and the vaccinated group has 0.90 probability of success then the power of

A Comprehensive Cancer Center Designated
by the National Cancer Institute

Phase: II

YCC Version 4.0 Date: 31-May-2017

pg. 21

our design is 0.78 at significance level 0.1. Patient deaths which are not related to influenza or disease progression will be censored for efficacy analysis.

Yale University's online OnCore system will be used to randomize the patients. Randomization will be performed by the clinical trials office of Yale University and the information released only to the research pharmacist.

We will monitor the study for the toxicity of the vaccine. The unacceptable toxicities include any serious adverse event grade 3 or higher which is believed to be related to the study vaccine. The tolerability will initially be tested in the first 20 patients in the vaccine arm. We will consider the vaccine tolerable if the rate of vaccine related toxicity is 10% or less and intolerable if 30% or more. If, in the first 20 patients, we observe 5 or more patients with vaccine related toxicity, then the cohort will be terminated early. With this design, the probability of terminating the cohort early is 0.04 if the true but unknown toxicity rate is 10% and 0.76 if the true rate is 30%.

Regulatory Considerations

Institutional Review Board/Ethics Committee approval

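### The 30% control failure rate adds two events that can occur in the same patient; on the stated inputs it is an upper bound, 28% under independence, which costs about 4 to 5 points of power

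*Combined protocol and SAP*

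**What the plan says.** The endpoint is defined under Biostatistical Considerations: "A patient is considered a treatment failure if either of the following events occur during the 2015-6 flu season". The two events are progression of the plasma cell disorder and any documented influenza infection. A patient with both is therefore one failure.

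The control rate is derived in Background and Rationale, under Rationale for Treatment in this Setting. Progression is put at 10%, described as "a conservative estimate of the proportion who would relapse from the time of initial vaccine to the end of the influenza season", and influenza at 20%. From these the text concludes: "we would expect our control arm to have a combined disease progression and influenza infection rate of 30% (10%+20". Nothing is said about patients who have both events.

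The complement of 30% becomes the planning value. The Protocol Synopsis states "we power for success rates of 90% and 70% in the experimental and control arms, respectively". Biostatistical Considerations repeats it ("If the standard care group has 0.70 probability of success") and reports power 0.93 against 0.90 in the vaccinated group, with 50 and 100 patients. A second example, 0.75 versus 0.90, has power 0.78 at significance level 0.1. Neither the test nor its sidedness is given.

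**The concern.** The probability that at least one of two events occurs is the sum of their probabilities minus the probability of both. Adding 10% and 20% sets that last term to zero. The protocol does not state or justify this, and its rationale points the other way: it puts forward the hypothesis that "exposure to common pathogens may itself contribute to promoting the growth of tumor cells", and that infection interrupts therapy and so compromises disease control. If that is so, the two events should coincide more often than chance.

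With the component rates fixed, ignoring overlap raises control failure, widens the assumed difference between arms and raises the stated power. What is at stake is the headline power for the primary endpoint.

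**Working it through.** **Inputs.** Control progression 10% and control influenza 20% (Rationale for Treatment in this Setting). Experimental success 0.90, sample sizes 50 and 100, alpha 0.10 (Biostatistical Considerations). Alpha is stated only with the second power example; I assume it applies to both.

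**Step 1: reproduce the plan's power.** Let p1 be control success, p2 experimental success and pb = (50 p1 + 100 p2)/150. Define

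- s0 = sqrt[pb(1 - pb)(1/50 + 1/100)]
- s1 = sqrt[p1(1 - p1)/50 + p2(1 - p2)/100]
- power = Phi[(p2 - p1 - c - z s0)/s1]

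where z = 1.645 for two-sided and 1.282 for one-sided 0.10. The correction c is 0, or 0.5(1/50 + 1/100) = 0.015 with continuity correction.

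For 0.70 versus 0.90: pb = 0.8333, s0 = 0.0645, s1 = 0.0714.

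- Two-sided, pooled normal: Phi(1.314) = 0.906
- One-sided, continuity-corrected: Phi(1.432) = 0.924
- Two-sided chi-square, power enumerated over the exact binomials: 0.914

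For 0.75 versus 0.90 the same three methods give 0.760, 0.793 and 0.766. The last two methods come within 2 points of both stated figures (0.93 and 0.78); the pooled normal misses 0.93 by 2.4 points. One-sided 0.10 without correction gives 0.950 and 0.850, and two-sided 0.05 (pooled) gives 0.848 and 0.664, so neither matches.

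**Step 2: composite control rate.** P(either) = 0.10 + 0.20 - P(both).

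| Overlap | P(both) | Control failure | Control success |
|---|---|---|---|
| None (the plan) | 0 | 30% | 0.70 |
| Independence | 0.10 x 0.20 = 0.02 | 1 - 0.90 x 0.80 = 28% | 0.72 |
| Half of progressors also have influenza | 0.05 | 25% | 0.75 |

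With the two rates fixed, no pattern of overlap gives more than 30%.

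**Step 3: power at 0.72 versus 0.90.** pb = 0.84, s0 = 0.0635, s1 = 0.0702.

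| Test at alpha 0.10 | 0.70 vs 0.90 | 0.72 vs 0.90 | Loss |
|---|---|---|---|
| Two-sided, pooled normal | 0.906 | 0.859 | 0.047 |
| Two-sided, enumerated chi-square | 0.914 | 0.868 | 0.046 |
| One-sided, continuity-corrected | 0.924 | 0.883 | 0.041 |

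**Step 4: progression rate that would restore 30% under independence.** 1 - (1 - x)(0.80) = 0.30 gives x = 1 - 0.70/0.80 = 12.5%.

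**The case against.** The strongest reply is that the 10% is a rough figure that the plan itself calls conservative, so the total may be about right although the sum is not. This stands. The same paragraph expects more than two thirds of patients to be relapsed or refractory, and cites times to progression of 9.9 and 7.3 months after the first and second therapies, with follow-up of roughly 4 to 8 months. If those times are treated as exponential medians (my assumption), 24% to 53% of relapsed patients would progress in that window. With two thirds relapsed and no progression in the rest, that is about 16% to 35% overall, above the 12.5% needed. A reader might infer that control success must be at least 72%, and so that 70% is too favourable. The documents do not support that: it requires the 10% and 20% to be exact and the two events not to be negatively associated.

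Second, the plan already shows a less favourable case. Its 0.75 versus 0.90 example, with power 0.78, lies beyond the independence value of 0.72. This also stands and limits the consequence, although the plan does not link that example to overlap.

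Third, a reader might let overlap run to its limit in the control arm, with every progressor also having influenza, and infer that power collapses. That moves control success to 0.80 while leaving the experimental arm at 0.90. On the protocol's own hypothesis, preventing influenza would also prevent progression, so both arms would move. As an illustration only: if every progression occurred in a patient with influenza, and the pilot's 4% influenza rate held in the experimental arm, success would be 0.80 versus 0.96. Power would then be 0.90 to 0.92 with the three tests above. The collapse comes from holding one arm fixed.

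**Conclusion.** The derivation is wrong for the endpoint as defined: 30% is the upper bound for the stated inputs, and independence gives 28%. The resulting loss of about 4 to 5 points, to a power of about 0.86 to 0.88, rests on four assumptions: 10% and 20% taken as given, independence, experimental success held at 0.90, and alpha 0.10 with one of the three tests shown.

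The whole distance from the stated 0.93 should not be charged to the addition. Under these tests the uncorrected 0.70 case already gives 0.906 to 0.924; that part of the gap reflects the unstated test and sidedness. Nor does the check establish that true control failure is below 30%. The severity is minor: a planning input is wrongly derived, while the endpoint, randomisation and enrolment target are unaffected.

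**What to change.** In Rationale for Treatment in this Setting, replace the sum with the union probability and state the overlap assumption: 28% under independence, lower if the events tend to coincide. Alternatively, keep 30% and justify a progression rate that supports it, such as 12.5% under independence.

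If the stated inputs are kept, make 0.72 versus 0.90 the main case in the Protocol Synopsis and in Biostatistical Considerations. Restate its power with the test and sidedness named, and keep 0.75 versus 0.90 as the sensitivity case, saying what overlap it represents (5 points, or half of progressors).

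The cost is a text change in three places and a slightly less favourable stated power, with no extra patients.

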HEMATOLOGY: ***[name], [name], [name], [name], [name], [name], [name], [name], [name]**

*Eligible to obtain informed consent

A Comprehensive Cancer Center Designated
by the National Cancer Institute

Phase: II

YCC Version 4.0 Date: 31-May-2017

pg. 5

Table of Contents

1. Protocol Synopsis.....	6
2. Schedule of Study	
Assessments.....	10
3. Background and Rationale	11
4. Study Objectives and End Points	14
5. Investigational Plan.....	14
6. Serious Adverse Events.....	18
7. Protocol Amendments and Deviations.....	19
8. Data Management.....	19
9. Biostatistical Considerations.....	20
10. References.....	23
11. Appendices.....	25
A. Correlative Studies and collection of research samples	

Protocol Synopsis

PROTOCOL SUMMARY: A Randomized, Placebo-Controlled Study utilizing high dose trivalent influenza vaccine dose with a booster compared to standard of care in patients with monoclonal gammopathies

STUDY INTERVENTION:	Fluzone® High-Dose vaccine with a 30 day booster dose
INDICATION:	All patients with a diagnosis of a monoclonal gammopathy
STUDY Type:	Randomized, double blind, placebo-controlled, Phase II Study

Background and Rationale:

Influenza is a major cause of morbidity in the US. Patients with monoclonal gammopathies are known to have increased risk of developing influenza. Furthermore, several of the medications (such as proteasome inhibitors), commonly used to treat these tumors, are known to further increase the risk of these tumors. Seasonal influenza vaccination has been shown to reduce influenza related morbidity and is approved for routine prophylaxis in US. In 2009, Fluzone® high-dose vaccine was FDA approved in 2009 for adults aged 65 and older based on the data regarding higher rates of seroprotection (defined as hemagglutination antibody inhibition (HAI) titer of 40 or higher).

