Sensing of pathogens by the immune system is mediated by family of distinct pattern recognition receptors (such as toll like receptors, TLRs) that then activate immune response. In the setting of tumors involving the immune cells themselves, such as multiple myeloma, tumor cells commonly express TLRs and signaling via TLRs has been shown to regulate the growth and survival of tumor cells. This has led to the hypothesis that exposure to common pathogens may itself contribute to promoting the growth of tumor cells. Unfortunately, these patients also have immune paresis and are at increased risk for infections. Prevention of major seasonal infections may therefore have major impact not only on infection-related morbidity, but also tumor growth. In addition to potentially direct effect on tumor cells, pathogen-related morbidity also leads to interruption of therapy, which may further compromise disease control. Thus, influenza infections may cause mortality directly or indirectly by interfering with disease control. By measuring all-cause mortality at the end of an influenza season it is possible to account for all possible effects of influenza which may be related to mortality.

Although seasonal influenza vaccination is routinely employed in patients with monoclonal gammopathies, the data about its efficacy in this setting are limited and very few studies have specifically focused on this population. This is particularly true in the setting of newer agents that further reduce B cell function. Existing data suggest that routine seasonal influenza vaccination is not very effective in this population, with seroconversion rates of <20%. One approach to enhancing the efficacy of vaccination is the use of boosters. In the past 2013-2014 flu season, Hahn et al gave a standard dose influenza booster vaccine after 30 days to 25 myeloma patients and noted a doubling of serologic protection (HAI titer ≥ 40) from 14% to 33%. This suggests that

A Comprehensive Cancer Center Designated
by the National Cancer Institute

Phase: II

YCC Version 4.0 Date: 31-May-2017

pg. 7

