Plasma cell dyscrasias or monoclonal gammopathies are a group of benign and malignant disorders consisting of monoclonal plasma cells which secrete monoclonal immunoglobulins¹. These disorders include the pre-malignant entity Monoclonal Gammopathy of Undetermined Significance (MGUS), asymptomatic / active multiple myeloma, asymptomatic / active Waldenström Macroglobulinemia (WM), solitary plasmacytoma, and primary amyloidosis. Patients with monoclonal gammopathies are routinely offered influenza vaccines however there is no evidence that they are effective in preventing infections.

Influenza Vaccination

Influenza is a major cause of morbidity in the US. The most vulnerable populations include adults over the age of 65 years, those with serious co-morbidities². A particularly vulnerable population are thought to be patients with hematologic malignancies, particularly multiple myeloma. A population based study in Sweden of over 9,000 myeloma patients, demonstrated that myeloma was associated with a 5.4 fold increased risk of contracting influenza infections relative to healthy controls³.

Clearance of viral infection and vaccine responses are dependent on cell mediated immunity(CMI). The most accepted serologic measurement of antibody protection following influenza vaccine administration is hemagglutination antibody inhibition (HAI) titer of 40 or higher. However, this cutoff corresponds to an estimated 50% clinical benefit of preventing influenza infections, based on studies in young healthy adults^{4,5}. It is believed that CMI declines with age, which may help explain why the elderly are more vulnerable to influenza infections. HAI titers have also been shown to be lower in the elderly compared to young adults⁶. Based on studies showing increased serologic protection, Fluzone® high-dose vaccine was FDA approved in 2009 for adults aged 65 and older.

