Patients with plasma cell dyscrasias are known to have depressed immune function. Studies in myeloma have shown B cell dysfunction (hypogammaglobulinemia), functional abnormalities of dendritic and T cells, inversion of T cell CD4:CD8 ratio, abnormal T cell Th1/Th2 CD4⁺ ratio, and dysfunction of natural killer cells^{7,8,9}. Anti-cancer medications can further adversely affect the immune system. It is known that patients who received chemotherapy within 7 days of trivalent inactivated influenza vaccine have poorer responses¹⁰. There is no published data regarding the effects of more commonly used novel agents such as IMIDs and proteasome inhibitors on vaccine responses.

Several studies have demonstrated a poor serologic antibody response in those patients included with myeloma and WM. However, there is a paucity of prospective trials focusing exclusively on patients with monoclonal gammopathies. No studies have specifically investigated influenza

A Comprehensive Cancer Center Designated
by the National Cancer Institute

Phase: II

YCC Version 4.0 Date: 31-May-2017

pg. 12

immunity in precursor states such as MGUS, although these patients may have similar risks of unresponsiveness to influenza vaccine and are known to have hypogammaglobulinemia. Based on available trial data restricted to myeloma patients, serologic protection (HAI titer ≥ 40) to all three influenza strains following trivalent influenza vaccine is achieved in less than 20% of myeloma patients in each trial^{11, 12, 13}. There have been two trials investigating the benefit of booster vaccine in myeloma patients. In 2005 Ljungmen et al, studied 70 patients with hematologic malignancies (10 with myeloma and 4 with WM) and administered a booster dose 30 days following standard influenza vaccine booster and found no increase in serologic protection¹⁴. More recently, in the past 2013-2014 flu season, Hahn et al gave a standard dose influenza booster vaccine after 30 days to 25 myeloma patients and noted a doubling of serologic protection (HAI titer ≥ 40) from 14% to 33%¹⁵. This suggests that there may be a role for booster vaccines in patients with hematologic malignancies, however there is obviously much room to improve.

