By comparing this experimental approach directly to standard of care, data from estimates of effectiveness will inform the design of larger future controlled studies. As such, the data from this study can lead to practice-changing results. The data on immune correlates will also yield important information about in vivo “immune-competence” of these individuals, which in turn is important to design trials with emerging immune therapies.

Study Objectives

Endpoints

Primary endpoints

The primary clinical endpoint of this study is to measure a composite of documented influenza infection rate and disease progression (as defined by International Myeloma Working Group criteria) at the end of the flu season following a high dose influenza vaccine booster strategy versus standard of care. Please see sections under biostatistical considerations for details.

Secondary study endpoints

The secondary endpoints are 1) rates of serologic protection (defined as HAI titer >40) following Fluzone® High-Dose influenza vaccine after booster dosing and 2) measurement of T cell subsets and flu-specific T cell responses.

Investigational Plan

Study vaccine description

Fluzone® High-Dose

A Comprehensive Cancer Center Designated
by the National Cancer Institute

Phase: II

YCC Version 4.0 Date: 31-May-2017

pg. 15

Proper Name: Influenza Virus Vaccine

Trade Name: Fluzone® High-Dose Vaccine

Manufactuer: Sanofi Pasteur, Inc, License #1725

Indication: Fluzone High-Dose is indicated for active immunization of persons 65 years of age and older against influenza disease caused by influenza virus subtypes A and type B contained in the vaccine.

Fluzone (Influenza Virus Vaccine) for intramuscular injection is an inactivated influenza virus vaccine, prepared from influenza viruses propagated in embryonated chicken eggs. The virus-containing allantoic fluid is harvested and inactivated with formaldehyde. Influenza virus is concentrated and purified in a linear sucrose density gradient solution using a continuous flow centrifuge. The virus is then chemically disrupted using a nonionic surfactant, Octylphenol Ethoxylate (Triton®X-100), producing a “split virus”.

The split virus is further purified and then suspended in sodium phosphate buffered isotonic sodium chloride solution.

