Fluzone is standardized according to United States Public Health Service requirements and is formulated to contain HA of each of the following three influenza strains recommended for the current influenza season, including two A subtypes (H3N2 / H1N1) and one influenza B subtype.

Dosage form

Fluzone® High Dose is supplied in 0.5 mL for intramuscular injection

Adverse events:

In adults 18 through 64 years of age, the most common injection-site reaction was pain (>50%); the most common solicited systemic adverse events were headache and myalgia (>30%).

In adults >65 years of age, the most common injection-site reaction was pain (>20%); the most common solicited systemic adverse events were headache, myalgia, and malaise (>10%).

Post Marketing Experience

The following events have been spontaneously reported during the post-approval use of Fluzone.

- Blood and Lymphatic System Disorders: Thrombocytopenia, lymphadenopathy.
- Immune System Disorders: Anaphylaxis, other allergic/hypersensitivity reactions (including urticaria, angioedema)
- Eye Disorders: Ocular hyperemia

A Comprehensive Cancer Center Designated
by the National Cancer Institute

Phase: II

YCC Version 4.0 Date: 31-May-2017

pg. 16

- Nervous System Disorders: Guillain-Barré syndrome (GBS), convulsions, febrile convulsions, myelitis (including encephalomyelitis and transverse myelitis), facial palsy (Bell's palsy), optic neuritis/neuropathy, brachial neuritis, syncope (shortly after vaccination), dizziness, paresthesia
- Vascular Disorders: Vasculitis, vasodilatation/flushing•
- Respiratory, Thoracic and Mediastinal Disorders: Dyspnea, pharyngitis, rhinitis, cough, wheezing, throat tightness
- Skin and Subcutaneous Tissue Disorders: Stevens-Johnson syndrome
- General Disorders and Administration Site Conditions: Pruritus, asthenia/fatigue, pain in extremities, chest pain
- Gastrointestinal Disorders: Vomiting

Screening and Eligibility

The Investigator is responsible for keeping a record of all subjects who sign an Informed Consent Form for entry into the study. All subjects will be screened for eligibility. Screening procedures are outlined in Section 2, Schedule of Study Assessments and may take place on or < 30 days before the day of first vaccine administration.

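### The secondary endpoint counts serologic protection at HAI >40, while the protocol's own description of protection and its benchmarks count a titer of exactly 40 as protected

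*Combined protocol and SAP*

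**What the plan says.** The endpoint is defined in two places, and they agree. Study Objectives, under Secondary study endpoints, has "rates of serologic protection (defined as HAI titer >40". The Synopsis, under Study Endpoints, has "evaluate rates of serologic protection (defined as HAI titer >40".

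Every other HAI cut-off in the document includes 40:

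- The Synopsis background, on the data behind approval of the high-dose vaccine: "seroprotection (defined as hemagglutination antibody inhibition (HAI) titer of 40 or higher".
- Background and Rationale, Influenza Vaccination, on the generally accepted measure: "hemagglutination antibody inhibition (HAI) titer of 40 or higher".
- The Synopsis and the Influenza Vaccination section, on a booster study in 25 myeloma patients: "doubling of serologic protection (HAI titer ≥ 40) from 14% to 33"%.
- The Influenza Vaccination section, on earlier trials of a single vaccination: "serologic protection (HAI titer ≥ 40) to all three influenza strains following trivalent influenza vaccine is achieved in less than 20% of myeloma patients".

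The vaccine description says that the product is "formulated to contain HA of each of the following three influenza strains". Neither endpoint statement says whether the cut-off applies to each strain or to all three. Appendix A lists HAI titers against influenza A and B, with no cut-off and no dilution series. Biostatistical Considerations does not mention the serologic endpoint.

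**The concern.** A patient whose titer is exactly 40 is unprotected under the endpoint as worded. The same patient is protected under the measure that the protocol itself calls the accepted one, and under the published rates that it uses to motivate the trial. No section says that a stricter threshold was intended.

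What is at stake is the meaning of the reported rate. A reader will naturally set the trial's protection rates beside the 14%, 33% and below-20% figures. If the trial's rates are counted at >40, they are not on the same scale, and any gap runs in one direction: the trial's rates can only look lower. The below-20% figure has a second condition attached, because it is protection against all three strains at once. Correcting the sign alone would not make a single-strain rate comparable with it.

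**Working it through.** The plan gives no sample size, power or significance level for serology, so there is no stated figure to reproduce. The check is a comparison of definitions, followed by the arithmetic that they imply.

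**Inputs.** Cut-offs as listed above. Arm sizes of 100 (vaccine) and 50 (control), from Screening and Eligibility and Biostatistical Considerations. Assumption: every randomized patient has a post-booster titer. With fewer titers, the steps below are larger.

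**1. Relation between the two rates.**

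Rate at >40 = rate at ≥40 − share of patients whose status changes.

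The share cannot be negative, so the rate at >40 is never higher. The documents give no titer distribution, so the share is unknown. Its minimum is 0.

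**2. Step per patient, scored strain by strain.** Each patient at exactly 40 on a strain lowers that strain's rate by:

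- vaccine arm: 1/100 = 1.0 percentage point;
- control arm: 1/50 = 2.0 percentage points.

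**3. Step per patient, all three strains required.** A patient at exactly 40 on one strain and below 40 on another is unprotected at either cut-off, so nothing changes. Status changes only for a patient at ≥40 on all three strains with at least one of them at exactly 40. Each such patient moves the rate by the same 1.0 or 2.0 points.

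**4. Difference between arms.**

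Difference at >40 = difference at ≥40 − (share changing in vaccine arm − share changing in control arm).

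The difference moves only if those two shares differ. The documents do not say that they would, or in which direction.

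**5. Comparison with the below-20% figure.**

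P(protected on all three strains) ≤ the lowest of the three single-strain rates.

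A single-strain rate set beside an all-three-strain benchmark can therefore look better than it is, whichever sign is used. The strain basis of the 14% and 33% figures is not stated.

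**The case against.** **The sign may have been lost when the PDF was read.** This is the strongest objection. The vaccine's adverse-event text, straight after a group aged 18 through 64, reads "In adults >65 years of age, the most common injection-site reaction was pain". That leaves age 65 in neither group and suggests a dropped or loosely typed sign. The two endpoint statements may also share a source, so they are not fully independent evidence. On the other side, ≥ survives in the Synopsis background, in the Influenza Vaccination and Rationale sections and in section 5.4.1, while >40 appears in both endpoint statements. Loss is possible but not shown. What stands is that the source file must be checked before anything is changed.

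**The background does not define this trial's endpoint.** This is correct. Those sections describe an approval, a general convention and other studies' results. A reader might infer that the plan gives two rival definitions of its endpoint; it does not, because the two endpoint statements agree. The conflict is between the endpoint and the standard that the protocol invokes for it, and it remains unexplained.

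**The harm is indirect.** This also stands. The Synopsis frames the endpoint as a comparison with standard of care, no test against the published rates is planned, and the ≥40 rate can be recovered from the measured titers.

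**A reader might infer a large loss.** Assuming two-fold dilutions with a reading at 40, and log2-normal titers with a standard deviation of 1 to 2, a 33% rate at ≥40 would become about 8% to 17% at >40. The documents support neither assumption, so this is an illustration and not an estimate.

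**Conclusion.** The concern holds as a minor inconsistency, conditional on the printed sign being >. Taken literally, the endpoint scores a titer of exactly 40 against the protocol's own description of protection. The resulting rate is at most the ≥40 rate and is not comparable with the quoted benchmarks.

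The total effect cannot be estimated from the documents. It is zero if no patient meets the condition for changing status under the scoring rule used. The per-patient steps of 1.0 and 2.0 points rest on full arms of 100 and 50 with titers available.

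A reader might infer that the treatment comparison is biased. The documents do not support that: both arms are scored by one rule, and nothing indicates unequal shares at exactly 40. The primary composite endpoint and its power are unaffected.

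**What to change.** 1. Check the printed sign in the source file at both endpoint statements. If it is ≥, the sign point falls away.
2. If it is >, change both statements (Synopsis, Study Endpoints; Study Objectives, Secondary study endpoints) to HAI titer ≥40.
3. Record the date and reason. This version is dated 31 May 2017, after the end-of-study draw window of 1 to 15 May 2016. If titers by arm had already been seen, report the rates at both cut-offs.
4. State whether protection is scored per strain or for all three, and report the all-three-strain rate wherever the below-20% benchmark is used.

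The cost is one sign in two places, one clause on strains and one dated note. No new patient, visit or sample is needed.
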